# 8.3.2.3. All Other Safety Analysis

Summary statistics for all other safety analysis will be done using the Safety Population.

All AEs will be coded using the Medical Dictionary for Regulatory Activities (MedDRA) and characterized as pre-treatment and treatment-emergent according to the intake of the study drugs. The occurrence and incidence of TEAEs will be summarized by MedDRA system organ class and preferred term and by treatment. The occurrence and incidence of TEAEs will also be summarized by severity and by relationship to the study drugs. Adverse events leading to discontinuation and SAEs will be listed.

Clinical laboratory parameters will be summarized by visit using descriptive statistics. Values within and outside the reference range will also be summarized using frequency tablets. Vital sign and ECG parameters and change from baseline (predose) will be summarized at each time point by treatment using descriptive statistics. Physical examination abnormalities and C-SSRS findings will be listed.

## 8.4. Pharmacokinetics

The PK analysis will be carried out according to AZ SOPs. Pharmacokinetic data handling and analysis will be further detailed in a SAP.

# 8.4.1. Pharmacokinetic Parameters

The PK parameters will be determined by non-compartmental analysis using appropriate software. The PK parameters for AZD4041, morphine, morphine-6-glucuronide and morphine-3-glucuronide are presented in Table 8-1.

Parameter a	Definition		
For morphin	For morphine, morphine-6-glucuronide and morphine-3-glucuronide (Day 1 and 15)		
C max	Maximum observed concentration occurring at time t max		
t max	Time of maximum observed concentration. If the maximum observed concentration is not unique, then the first maximum is used		
AUC 0-t	Area under the concentration time curve from the time of last dosing to the time of last quantifiable concentration $(T_{last})$		
AUC 0-∞	Area under the concentration time curve extrapolated to infinity, calculated as $AUC_{0-T} + C_{last}/\lambda_Z$ , where $C_{last}$ is the last quantifiable concentration at time $T_{last}$		
t 1/2,z	Terminal elimination half-life, calculated as $ln(2)/\lambda$		

 Table 8-1 Pharmacokinetic Parameters in Plasma

Parameter a	Definition		
T last	Time of last measurable observed concentration		
CL	Total body clearance, calculated as $Dose/AUC_{0-\infty}$ (parent drug only)		
Vz	Volume of distribution based on terminal phase (parent drug only)		
	For AZD4041		
Days 2 to 7 and Days 9 to 14:			
Ctrough	Predose concentration observed immediately prior to the next successive dose		
Days 8 and 15			
C max,ss	maximum observed plasma concentration		
t max,ss	time to maximum observed plasma concentration		
C trough	Predose concentration observed immediately prior to the next successive dose		
AUC τ	area under the concentration time curve over the dosing interval at steady- state, calculated from 0 to 24 hours (dosing interval)		
C av	average concentration during a dosing interval, after the last dose of a multiple dose regimen, calculated as AUC $\tau/\tau$		
t 1/2,z	Terminal elimination half-life, calculated as $ln(2)/\lambda_z$ (Day 15 only)		
CLss/F	Apparent total body clearance at steady-state, calculated as $Dose/AUC_{\tau}$		
Vzss/F	Apparent volume of distribution at steady-state, based on terminal phase		

a. A complete list of PK parameters that will be used for PK calculation and presented in the PK listings will be included in the SAP.

Parameter	Definition
Ает	Amount of drug excreted in urine. The Ae at each urine collection interval will be calculated as follows: Concentration * Volume of urine during that time interval (t1 to t2). Cumulative Ae will be calculated as the sum of all urine collection interval Aes. Note: The Ae at predose will not be included in the calculation of cumulative Ae.
fet	Cumulative fraction of unchanged drug excreted in urine over the dosing interval, calculated as (Aet/Dose)*100 (expressed in %), where Aet is the amount of drug excreted in urine during the dosing interval. Note: The Ae at predose will not be included in the calculation of fe.
CL R	Apparent renal clearance, calculated as $Ae\tau/AUC\tau$ on Day 15. A different time interval may be used providing not all single intervals are usable.
t1/2	Elimination half-life, calculated as $ln(2)/\lambda z$ on Day 15

# Table 8.2 Pharmacokinetic Parameters in Urine for AZD4041 (Day 15 only)

#### 8.4.2. Summary and Presentation of PK data

- The plasma and urine concentration data for all the analytes will be presented individually and summarized by time point by day for each treatment
- The PK parameters data for all the analytes will be presented individually and summarized by day for each treatment
- Individual as well as mean plasma and urine concentration versus time plots will be presented by day for AZD4041 as well as morphine and its metabolites (together) separately

## 8.4.3. Pharmacokinetic Statistical Methodology

## 8.4.3.1. Assessment of Steady State Achievement

Ctrough will be compared descriptively to assess the achievement of steady-state for AZD4041.

## 8.4.3.2. Comparison of PK Parameters

Two-sided 90% confidence interval of the ratio of geometric LSmeans obtained from the ln-transformed PK parameters ( $C_{max}$ , AUC0-t, and AUC0- $\infty$  for morphine and its metabolites;  $C_{max,ss}$  and AUC $\tau$  for AZD4041) will be calculated to assess the magnitude of interaction for the following comparisons:

- Morphine and its metabolites: Morphine + AZD4041 (Day 15) versus Morphine alone (Day 1)
- 2. AZD4041: Morphine + AZD4041 (Day 15) *versus* AZD4041 (Day 8)

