	Neurological examination findings
	C-SSRS findings
	• Type of medical intervention used, summarized for each event of significantly increased EtCO 2 , reduced SpO 2 , or respiratory rate
To assess the PK of AZD4041 and morphine in healthy recreational opioid users	Plasma concentrations as well as PK parameters for AZD4041 and morphine and its metabolites as described in Section 8.4
To assess the impact of multiple dose administrations of AZD4041 on the PK of morphine and its metabolites	Plasma concentrations as well as PK parameters for AZD4041 and morphine and its metabolites as described in Section 8.4
To assess the impact of morphine on steady-state PK of AZD4041	Plasma concentrations as well as PK parameters for AZD4041 and morphine and its metabolites as described in Section 8.4
To assess the renal clearance of AZD4041	Urine concentrations as well as PK parameters for AZD4041 as described in Section 8.4

Abbreviations: AE = adverse event; C-SSRS = Columbia-Suicide Severity Rating Scale; ECG = electrocardiogram EtCO2 = end tidal carbon dioxide; PK = pharmacokinetic; SpO2 = oxygen saturation.

[figure not shown]

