## 3. STUDY DESIGN

#### **3.1. Overall Study Design**

This is a Phase 1, randomized, double-blind, placebo-controlled, 2 fixed sequences, multiple dose study in healthy male and/or female recreational opioid users.

This study will consist of 3 phases: Screening and Qualification, Treatment phase, and Follow-up (see Figure 3-1).

After a Screening period of up to 27 days (Day -30 to Day -3), eligible subjects will be admitted to the clinical research unit (CRU) on Day -2. Subjects will be randomized to 1 of 2 fixed treatment sequences (28 subjects in Sequence 1, and 16 subjects in Sequence 2) on Day -1.

Subjects will be required to present a negative urine drug and alcohol screen upon admission on Day-2, except for tetrahydrocannabinol (THC). If THC is positive at admission, a cannabis intoxication evaluation will be done by an Investigator, and subjects may be permitted to continue in the study at the discretion of an Investigator. Subjects will then undergo a naloxone challenge where an initial 0.2 mg intravenous (IV) dose of naloxone hydrochloride (HCl) will be administered. The subject will be observed for signs or symptoms of opioid withdrawal. If there is no evidence of withdrawal within 1 minute (as assessed by a Clinical Opioid Withdrawal Scale [COWS] score of <5), an additional 0.6 mg IV dose of naloxone HCl will be given, and the subject will be observed for signs and symptoms of withdrawal for 5 minutes (as assessed by COWS). Subjects who present symptoms of withdrawal during the qualification process will be excluded from the study and will not be eligible to enter the Treatment phase.

In total, subjects will be confined to the CRU for approximately 20 days from Day -2 to Day 18 (until approximately 72 hours following the last study drug administration).

On Day 1, subjects will receive a single CCI IV dose of morphine. From Day 2 to Day 15, subjects will receive a CCI oral dose of AZD4041 or placebo once daily for 14 consecutive days. On the morning of Day 15, the CCI oral dose of AZD4041 or placebo will be combined with a single CCI IV dose of morphine.

In order to limit the number of subjects being treated with investigational product (IP) on any single day, eligible subjects should be assigned to different subgroups. Subgroup sizes should be limited to no more than 8 subjects. Dosing of subgroups should be staggered to occur on different days, with at least 2 days between the start of dosing for sequential subgroups.

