8.5.2 PK Parameter Descriptive Statistics

All PK parameters are summarised for each analyte by PK Day and Treatment sequence using appropriate descriptive statistics. Similar parameter data (e.g. single dose or multiple dose for the same dosing regimen) from different PK Days may also be summarised together.

The descriptive statistics for PK parameters are presented as follows:

- Ctrough, Cmax, Cmax,ss, Cav, AUC τ , AUC0-t, AUC0- ∞ , $t^{1/2}\lambda z$, CL, CLss/F, Vz, Vzss/F, CLR, Ae and fe: present n, geometric mean, geometric standard deviation (Geo Std Dev), arithmetic mean of non log-transformed data (mean), arithmetic standard deviation (Std Dev), gCV(%), median, min and max.
- tmax, and tlast: present n, median, min and max.
- Diagnostic parameters (e.g. λz , λz lower, λz upper, λzN , λz span ratio, n obs, Rsq adj and AUCextr): present n, arithmetic mean, Std Dev, gmean, gCV%, median, min and max.

Three values are required as a minimum for PK parameters to be summarised. Two values are presented as a min and max with the other summary statistics as NC.

If one or more values for a given parameter is zero, then no geometric statistics are calculated for that parameter and the results for geometric statistics are set to NA (Not Applicable).

The point estimate and associated two-sided 90% confidence intervals for the ratio of PK parameters (for AZD4041: AUC τ , Cmax,ss, Ctrough,ss; for morphine and metabolites: Cmax, AUC0-t, AUC0- ∞) for each comparison of interest will be calculated:

For treatment sequence 1:

- AZD4041 in the absence of Morphine - Day 8 and AZD4041 in the presence of Morphine – Day 15
- Morphine in the absence of AZD4041 – Day 1 and Morphine in the presence of AZD4041 – Day 15
- Morphine metabolites in the absence of AZD4041 – Day 1 and Morphine metabolites in the presence of AZD4041 – Day 15

For treatment sequence 2:

- Morphine on Day 1 and 15.
- Morphine metabolites on Day 1 and 15.

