For EtCO₂, SpO₂, and respiratory rate the following figures will be generated:

- 1) Sequence 1: Mean (\pm SD) treatment by time point for Day 1 Morphine alone matched to Day 15 Morphine + AZD4041
- 2) Sequence 2: Mean (\pm SD) treatment by time point for Day 1 Morphine alone matched to Day 15 Morphine + Placebo
- 3) Mean (\pm SD) treatment by time point for Days 2-15 predose AZD4041 vs. Days 2-15 predose Placebo
- 4) Boxplot for E_{max} Day 1 Morphine alone matched to Day 15 Morphine + AZD4041
- 5) Boxplot for E_{max} Day 1 Morphine alone matched to Day 15 Morphine + Placebo
- 6) Boxplot for E_{max} Day 15 Morphine + AZD4041 vs. Day 15 Morphine + Placebo

For all inferential analysis on EtCO₂, SpO₂, and respiratory rate, mixed-effects models will be used for E_{max} and averaged measures. The models will include sequence, time (as a ordered factor variable), and the sequence-by-time interaction as fixed effects and baseline as a covariate, with 95% confidence intervals reported along with p-values. Homogeneity of treatment variances will be explored to determine if subject may be considered a random effect. The covariance structure for the mixed models will be heterogeneous compound symmetry. If the heterogeneous compound symmetry model does not converge, then a compound symmetry structure will be used and a footnote will be added to identify the results as using a different covariance structure than usual. The kenwood-roger adjustment for the degrees of freedom will be used when calculating p-values due to the small sample size.

The maximum postdose decrease in respiratory rate (E_{max (predose - postdose)}) is the primary criterion. In addition to the primary criterion, maximum postdose reduction in SpO₂ (E_{max (predose - postdose)}) and The maximum postdose increase in EtCO₂ (E_{max (postdose - predose)}) will have the following contrasts calculated in the mixed-effects models:

- 1) Morphine + AZD4041 (Day 15) vs Morphine alone (Day 1) [Sequence 1]
- 2) Morphine + Placebo (Day 15) vs Morphine alone (Day 1) [Sequence 2]
- 3) Morphine + AZD4041 (Day 15) vs Morphine + Placebo (Day 15) [Sequence 1 vs Sequence 2]

For EtCO₂, SpO₂, and respiratory rate averages (predose average from Days 2 to 15), and postdose average on Day 15, the following contrasts will be explored in the mixed-effects models:

- 1) (postdose): Morphine + AZD4041 (postdose average Day 15) vs (predose): AZD40401 (predose average Days 2-15)

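### The plan reports the morphine PK ratio (Day 15/Day 1) separately in the AZD4041 and placebo sequences but never contrasts the two, so a shift common to both stays inside the interaction estimate

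*Protocol*

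**What the plan says.** - **Objective.** Protocol section 2 lists as a secondary objective: "To assess the impact of multiple dose administrations of AZD4041 on the PK of morphine and its metabolites".
- **Protocol 8.4.3.2.** The statistic is a "Two-sided 90% confidence interval of the ratio of geometric LSmeans obtained from the ln-transformed PK parameters" (Cmax, AUC0-t and AUC0-∞ for morphine and its metabolites), which "will be calculated to assess the magnitude of interaction for the following comparisons". For these analytes one comparison is listed: morphine with AZD4041 on Day 15 against morphine alone on Day 1. Only Sequence 1 supplies it.
- **SAP 8.5.2.** "The point estimate and associated two-sided 90% confidence intervals for the ratio of PK parameters" are to be calculated for each comparison of interest. For Sequence 1 these include the Day 1 and Day 15 comparison above. For Sequence 2 the SAP adds "Morphine on Day 1 and 15", and the same for the metabolites. SAP 8.5.3 plots the estimates and intervals for every comparison.
- **What is absent.** Neither document lists a Sequence 1 versus Sequence 2 contrast for PK, a sequence-by-day term in a PK model, or a statement of how the Sequence 2 ratio enters the interaction conclusion.
- **Contrast with the respiratory analysis.** SAP 9.1 fits sequence, time and their interaction for respiratory Emax, and compares the two sequences directly on Day 15.
- **Sampling.** Protocol Table 6-14 samples morphine and its metabolites to 36 h on Day 1 and to 72 h on Day 15. The time points up to 36 h are the same on both days.

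**The concern.** The objective asks what AZD4041 does to morphine exposure. A before-after ratio within Sequence 1 answers that only if nothing else moves the ratio between Day 1 and Day 15. Sequence 2 is the randomised control for that assumption: it has the same confinement, the same daily oral vehicle from Day 2 to Day 15 and the same morphine sampling, and lacks only AZD4041. The trial pays for this control and collects its paired profiles, then sets its result next to the Sequence 1 result without subtracting it.

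At stake is the reading of the Sequence 1 ratio. If both sequences show a ratio of, say, 1.10, the effect attributable to AZD4041 is nil, but the quantity that Protocol 8.4.3.2 uses to assess interaction is 1.10. A reader of the report would have to do the subtraction mentally and would have no interval for the result.

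AUC0-t deserves particular attention because the plan itself creates a difference between the days. AUC0-t runs to the last quantifiable concentration, and Day 15 allows another 36 h for that concentration to occur.

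**Working it through.** **Counts.** There is no sample-size formula or PK power to reproduce (Protocol 8.5, SAP 3.5). The counts agree: the SAP 3.4 blocks give 4 + 4×8 + 8 = 44, with 2 + 20 + 6 = 28 in Sequence 1 and 2 + 12 + 2 = 16 in Sequence 2. Planned completers are 24 + 12 = 36.

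**1. A common shift and the two estimates.** On the ln scale let θ be the AZD4041 effect and δ a Day 1 to Day 15 shift shared by both sequences.
- Sequence 1 ratio estimates θ + δ.
- Sequence 2 ratio estimates δ.
- Their difference (the ratio of ratios) estimates θ.

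**2. Size of the built-in sampling artefact.** Assume mono-exponential decline with half-life h, quantifiable to the last sample. Then

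AUC0-72/AUC0-36 = (1 − 2^(−72/h)) / (1 − 2^(−36/h)) = 1 + 2^(−36/h).

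| Assumed half-life | AUC0-72/AUC0-36 |
|---|---|
| 4 h | 1 + 2^(−9) = 1.00 |
| 8 h | 1 + 2^(−4.5) = 1.04 |
| 12 h | 1 + 2^(−3) = 1.13 |
| 24 h | 1 + 2^(−1.5) = 1.35 |

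The documents give neither half-lives for morphine, M6G and M3G nor assay limits, so this is a range and not a prediction. Cmax is unaffected.

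**3. Precision of the two estimates.** Inputs: 24 and 12 completers (Protocol 8.5), and an assumed within-subject CV of 15% to 30%, which the documents do not give.
- SD of a paired ln difference = √(2 ln(1 + CV²)).
- SE, Sequence 1 = SD × √(1/24), t with 23 df.
- SE, ratio of ratios = SD × √(1/24 + 1/12), pooled t with 34 df.
- SE ratio = √((1/24 + 1/12)/(1/24)) = √3 = 1.73, whatever the CV.

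At CV 20%: SD = √(2 × ln 1.04) = 0.280. The SEs are 0.057 and 0.099. The 90% half-widths are 1.714 × 0.057 = 0.098 and 1.691 × 0.099 = 0.167, that is, factors of 1.10 and 1.18.

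| CV | Sequence 1 ratio, 90% CI around 1.00 | Ratio of ratios, 90% CI around 1.00 |
|---|---|---|
| 15% | 0.93–1.08 | 0.88–1.13 |
| 20% | 0.91–1.10 | 0.85–1.18 |
| 25% | 0.89–1.13 | 0.81–1.23 |
| 30% | 0.87–1.16 | 0.78–1.28 |

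**4. When the controlled estimate is the better one.** Mean squared error is δ² + SD²/24 for the Sequence 1 ratio and SD² × (1/24 + 1/12) for the ratio of ratios. The second is smaller when δ > SD × √(1/12). With SD = 0.211, 0.280 and 0.415 at CV 15%, 20% and 30%, the threshold is 0.061, 0.081 and 0.120, that is, a shared shift of about 6%, 8% and 13%.

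**The case against.** The strongest reply is that the SAP already handles much of this. It calculates the placebo-sequence ratio with a 90% CI for the same parameters and plots it alongside. A large common shift would be visible. That stands. A reader might infer that the plan ignores the placebo sequence, or that every time, confinement or vehicle effect will be counted as an AZD4041 interaction. SAP 8.5.2 and 8.5.3 do not support that. What remains is that two intervals side by side give neither an estimate nor an interval for their difference, and no rule says how to read them together.

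Second, a shift is largely hypothetical. Morphine is infused over 10 minutes on both days, subjects fast on both, and alcohol and xanthines are barred from 48 h before first dosing onward. Admission rules are not identical to Day 15 conditions (for a positive THC test, "subjects may be permitted to continue in the study at the discretion of an Investigator"), but neither document links THC, confinement or the vehicle to morphine PK. That also stands. The sampling difference is the one source visible in the plan, and its size is unknown.

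Third, the controlled estimate rests on 12 placebo completers and is noisier. By step 4 it has the larger mean squared error if the shared shift is small. This is a good reason not to replace the planned ratio.

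Two further inferences are tempting. One is a false-signal rate: with a shared 10% shift, no interaction and CV 20%, the Sequence 1 90% CI would exclude 1 in about 49% of trials instead of 10%. Neither document makes exclusion of 1 a decision rule, and the 10% is assumed, so this is the error rate of a test that nobody planned. The other is that the respiratory result would be assigned to the wrong mechanism. SAP 9.1 already compares the sequences on Day 15, where an exposure shift common to both cancels, and no analysis is planned that explains that contrast through the PK ratio.

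**Conclusion.** The gap is real and limited. The effect of AZD4041 on morphine PK is assessed by an uncontrolled before-after ratio, while the randomised control ratio is reported separately and never contrasted with it. A shared shift passes in full into the Sequence 1 ratio. For AUC0-t one such shift can arise from the sampling schedule alone, from negligible at a 4 h half-life to 1.35-fold at 24 h.

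The conclusion that no between-sequence PK contrast is planned rests on the documents alone. The sizes rest on assumptions: the half-lives, quantifiability to the last sample, the within-subject CV, equal variance of the paired differences in the two sequences, and the magnitude of any shared shift. This is a cheap improvement to a secondary objective. It does not show that the planned estimate is wrong.

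**What to change.** Before database lock, add to SAP 8.5.2:

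1. For each of Cmax, AUC0-t and AUC0-∞ of morphine, M6G and M3G, a model on the ln scale with sequence, day, sequence-by-day and subject. Report the ratio of ratios (Day 15/Day 1 in Sequence 1 over Day 15/Day 1 in Sequence 2) with its 90% CI, beside the two within-sequence ratios and not in place of them.
2. One sentence saying how the Sequence 2 ratio and the ratio of ratios will be read when judging an interaction.
3. AUC over a common 0–36 h window on both days. This removes the difference in window length directly, while the ratio of ratios removes only the part that is equal in both sequences.

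The cost is SAP wording and a few lines of output, with no new data. The statistical price is the wider interval: a factor of 1.18 against 1.10 at CV 20%, and from 1.13 against 1.08 (CV 15%) to 1.28 against 1.16 (CV 30%). Timing matters because SAP 5.1 classes analyses done after lock or unblinding as post hoc and exploratory.

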## 8.5. Determination of Sample Size

No formal sample size calculation has been performed. The number of participants is based on the precedent set by other studies of similar nature (Verbekt et al, 2017). The number of

participants planned for completion in this study is considered sufficient to achieve the study objectives. Approximately 44 subjects will be randomized (28 AZD4041 + morphine and 16 Placebo + morphine) to complete at least 36 subjects (24 AZD4041 + morphine, and 12 Placebo + morphine on Day 15).

## **10. APPENDIX 1: ETHICS**

## **10.1. Institutional Review Board**

This protocol and the ICF will be submitted to an IRB (or Independent Ethics Committee[IEC]) prior to initiation of the study and the study will not start until the Board has approved the documents. Notification of the Board's approval will be appended to the final report.

## 10.2. Ethical Conduct of the Study

This study will be conducted in compliance with the study protocol, the ethical principles that have their origins in the Declaration of Helsinki, the International Council for Harmonisation (ICH) Guideline E6 for Good Clinical Practice (GCP), the FDA GCP Code of Federal Regulations (CFR) Title 21 (part 56), the EU Clinical Trial Directive (EC) No. 2001/20/EC, the European regulation EU 536/2014 and the Tri-Council Policy Statement (Canada).

